#### 4.4.3. Metabolic profiles

Samples will be obtained at baseline, 1 hour and 4 hours postprandial to be analyzed by the Metabolomics Core at Broad Institute. This Core has developed an LC-MS/MS methodology that uses several chromatographic stationary phases and analyzes > 400 sugars, sugar phosphates, nucleotides, amino acids, organic acids, and lipids (e.g. individual cholesterol esters, triglycerides, diacylglycerols, phospholipids, and lysophospholipids) in a targeted manner. The platform is designed on the principle that a metabolite can be identified by its parent ion mass (MS) and dominant product ion mass (MS/MS) on a sensitive mass spectrometer in combination with its retention time on an appropriate chromatography column. While none of these three parameters is individually sufficient to uniquely identify a metabolite in a biological fluid, the three in combination provide a “tag” that marks the metabolite to permit identification and quantification.

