### **Data Analyses**

#### **Endpoints**

Primary endpoint: Blood flow to the NAcc, as quantified by ASL.

Secondary endpoints: Blood flow to other brain areas relevant to intake control, connectivity of brain areas of intake control, metabolic fuels, hormones, hunger ratings, metabolomic profiles, ad libitum food intake.

Effect modifiers: insulin levels, glucose levels, metabolic fuels, hormones, hunger ratings, daily insulin requirement

Analysis of imaging data will be performed within the Statistical Parametric Mapping (SPM5, Wellcome Department of Cognitive Neurology) statistical image analysis environment. The images will be converted to a standard naming convention using the OSIRIX DICOM viewer (<http://homepage.mac.com/rossetantoine/osirix/Index2.html>) and then converted into Nifti format with appropriate spatial information in image headers. Once in the appropriate format, CBF images will be realigned to the first CBF image and then all CBF images will be transformed to a standard anatomical space using the registration parameters derived from the SPM "Normalization" algorithm applied to the mean image and using the gray matter a priori template as the target image. Normalization will be performed using the more standard preserve concentration option, which is acceptable since we do not expect significant atrophic changes during the study. Subsequently, images will be smoothed with an 8 mm FWHM kernel in preparation for statistical analysis. Statistical analysis will be performed on a voxel by voxel basis within SPM using the ANOVA algorithms of the general linear model and the SPM derived correction for multiple comparisons. A false discovery rate (FDR) threshold of 0.05 will be employed. Cluster size thresholding will not be initially employed to avoid loss of the small hypothalamus, but modest cluster thresholding may be applied to improve sensitivity of cortical activity change measurements. In addition, regional analysis of targeted regions will be performed by applying the regions defined with the AAL atlas on the spatially normalized images. MRI data will be correlated with data from venous sampling and hunger ratings using ANOVA algorithms.

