To address the primary and secondary hypotheses, we will employ methods appropriate to crossover trials. Hypotheses 1,2,4-8 will be tested by paired T-Test, controlling for baseline and meal order. Hypothesis 3 and 9 will be addressed by the Pearson correlation between brain activation parameters and calculated caloric intake. Secondary analyses of associations between brain activation, metabolic and psychophysical parameters will be performed using an ANOVA design. All tests will be conducted with a 5% Type I error rate. SAS software (Cary, NC) will be used for all computations.

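### The metabolomic profiles (more than 400 analytes) fall under the 5% per-test rule alone; the plan's false-discovery threshold covers only the voxelwise imaging analysis

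*Combined protocol and SAP*

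**What the plan says.** The Endpoints list under Data Analyses places the profiles among the secondary endpoints: "connectivity of brain areas of intake control, metabolic fuels, hormones, hunger ratings, metabolomic profiles, ad libitum food intake". Section 4.4.3 (Metabolic profiles) describes a platform that "analyzes > 400 sugars, sugar phosphates, nucleotides, amino acids, organic acids, and lipids", and gives the sampling times: "Samples will be obtained at baseline, 1 hour and 4 hours postprandial to be analyzed by the Metabolomics Core at Broad Institute".

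Multiplicity is addressed in three places:

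- The imaging paragraph under Endpoints: "Statistical analysis will be performed on a voxel by voxel basis within SPM", with SPM's own correction, followed by "A false discovery rate (FDR) threshold of 0.05 will be employed".
- The Multiple testing paragraph of the Sample Size Justification. It names one primary endpoint, treats the other hypotheses as secondary, and gives no correction for them.
- The closing paragraph of Data Analyses: "All tests will be conducted with a 5% Type I error rate".

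For metabolic data the only method named in that closing paragraph is an association analysis: "Secondary analyses of associations between brain activation, metabolic and psychophysical parameters will be performed using an ANOVA design". The same paragraph says "Hypothesis 3 and 9 will be addressed by the Pearson correlation between brain activation parameters and calculated caloric intake", after promising methods suited to crossover trials.

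**The concern.** The plan has two high-dimensional families, voxels and metabolites. It sets a false-discovery standard for the first and leaves the second to a per-test 5%. That rule limits the chance of a false call for any one metabolite. It does not limit the share of reported metabolites that are chance findings, and with several hundred tests that share is what a reader needs to know. If metabolites are tested singly, a list of significant ones would meet the plan's rule to the letter, yet nobody could say what fraction of it to believe.

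A smaller gap concerns Hypotheses 3 and 9. Each person has three test visits, each with imaging and a weighed meal, and the text does not say what one data point in the Pearson correlation is.

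**Working it through.** **Inputs from the documents.** n = 15; at least 400 metabolites (400 used as the lower bound); two contrasts (a vs b, b vs c); two postprandial time points (1 h, 4 h); 5% per test; 5% FDR for imaging; SD of the within-person difference 30 units; mean flow 548 units.

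**Assumed, because the documents give no figure.** One paired test per metabolite; 10, 25 or 50% of metabolites truly different; a true difference of 0.78 SD, with 0.5 and 1.2 SD as a range.

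**1. The plan's own figure.** (2.1448 + 0.868) × 30/√15 = 23.3 units, and 23.3/548 = 4.3%. This agrees with the plan. In SD units it is 23.3/30 = 0.78, the effect a paired test with n = 15 detects with 80% power. It is borrowed from blood flow as a reference size and is not an estimate for any metabolite.

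**2. All metabolites null.** 400 × 0.05 = 20 false calls per family. The simulated mean is 20.1, with a 95% range of 12 to 29 if metabolites are independent. If they are correlated (assumed blocks of 20 at r = 0.5), the range is 8 to 39.

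**3. Some metabolites truly different, 5% per test.** False share = false calls / (false + true calls), with 80% power:

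| Truly different | Expected false calls | Expected true calls | False share |
|---|---|---|---|
| 10% | 360 × 0.05 = 18 | 40 × 0.80 = 32 | 18/50 = 36% |
| 25% | 300 × 0.05 = 15 | 100 × 0.80 = 80 | 15/95 = 16% |
| 50% | 200 × 0.05 = 10 | 200 × 0.80 = 160 | 10/170 = 6% |

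The result depends on effect size. With 10% truly different, power is 44% at 0.5 SD and 99% at 1.2 SD, and the false share is 51% and 31%.

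**4. Benjamini-Hochberg at 5%.** For independent tests the expected false share is 5% times the null fraction: 0.05 × 0.90 = 4.5%, 0.05 × 0.75 = 3.75% and 0.05 × 0.50 = 2.5%. Simulation gives 4.6, 3.7 and 2.4%, and 4.4, 3.7 and 2.4% in the correlated blocks.

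**5. Power per metabolite when 10, 25 or 50% truly differ.**

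| True difference | 5% per test | Benjamini-Hochberg at 5% |
|---|---|---|
| 0.78 SD | 80% | 23, 44, 61% |
| 1.2 SD | 99% | 87, 95, 98% |

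The strictest step is 0.05/400 = 0.000125.

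**6. Hypotheses 3 and 9.** With 15 people and two visits each, and no true association, entering both visits as independent points gives a Type I error of 5.1, 5.5, 6.7, 9.3 and 13.2% at within-person correlations of 0, 0.2, 0.4, 0.6 and 0.8. These correlations are assumed equal for flow and intake. Using one value per person (a single condition, the person mean or a difference) gives 4.9 to 5.2%.

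**The case against.** The strongest reply is that the quantified harm belongs to an analysis the plan never states. No hypothesis in section B1 concerns a metabolite, paired t-tests are assigned to other hypotheses, and the figure of 400 describes what the platform can measure. This stands as a limit: the false-call figures are conditional on single-metabolite testing. The silence still matters. No multivariate method is named, and the 5% rule is written to cover every test.

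A reader might also infer 80 false findings (20 × 2 contrasts × 2 postprandial times). That would require every metabolite to be null in all four families, although the conditions are built to differ in insulin or in glucose. At the favourable end, with half the metabolites truly different by 0.78 SD, the false share at 5% per test is already only 6%.

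It is fair, too, that these are unpowered secondary outcomes in a study the protocol itself calls a pilot, and that FDR control costs power. Labelling the profiles exploratory and reporting the number of tests would give readers the all-null expectation of chance calls, but would not control the false share of a reported list.

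On Hypotheses 3 and 9, a reader might infer that visits will be pooled and Type I error inflated to 13%. The documents do not support that. They do not say visits will be pooled, and a crossover-appropriate method would avoid it. A reader might also want the baseline and order control stated for Hypotheses 1, 2 and 4 to 8 extended here. The plan does not call for it, and it is not clearly an improvement. With an assumed r = 0.7 and a stable between-person association, adding baseline control to a sequence-adjusted person-mean test cuts power from 40 to 12% (within-person correlation 0.5) or from 71 to 9% (0.8).

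**Conclusion.** The gap is real and cheap to close. No false-discovery rule reaches the metabolomic profiles, and the rule that does reach them leaves the false share of a reported list uncontrolled. If metabolites are tested singly, expect about 20 false calls per 400 nulls in each family. At an assumed 0.78 SD, the false share is about 36, 16 or 6% when 10, 25 or 50% truly differ, against about 5, 4 or 2.5% with Benjamini-Hochberg. The absence of a rule is certain from the text. The size of the harm rests on single-metabolite testing, the assumed effect size and the assumed share of true differences.

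This does not mean that the plan breaches its own 5% rate, which is met test by test, or that the primary comparison is in doubt. The Hypothesis 3 and 9 point is missing detail and not a demonstrated error.

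**What to change.** In the closing paragraph of Data Analyses, except the metabolomic profiles from the 5% per-test rule. Apply Benjamini-Hochberg at an FDR of 5%, matching the imaging threshold, across metabolites within each family. Define a family as:

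- each condition contrast (a vs b, b vs c) at each time point; and
- for association analyses, each brain or rating measure at each time point.

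The second line is needed because association is the one metabolic analysis the closing paragraph names. Report the number of metabolites tested. The per-test 5% rule stays for the endpoints it now governs, and the imaging threshold is unchanged.

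The cost is a few sentences, minor SAS programming and fewer metabolites called, with the power loss shown in step 5 of the working. If that is judged too strict, an FDR of 10% stated in advance would give about 40, 62 and 77% power at 0.78 SD.

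As a minor clarification, add one sentence that repeated visits of one person do not enter the Hypothesis 3 and 9 Pearson tests as independent points.

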### **C. Subject Selection**

#### **Inclusion criteria**

- Males age 18 to 45 years
- Type 1 diabetes for a minimum of 3 years
- BMI 20-35 kg/m^2
- Use of insulin pump
- Willing and able to: Maintain weight and document for duration of the study

Rationale for inclusion criteria. **Age:** We have chosen an age-range to minimize developmental and puberty effects on insulin sensitivity and brain activation, yet capture a relevant age-group for preventive measures where comorbidity isn't yet highly prevalent. **Gender** is a known confounder of neuroimaging data. Women with T1D are more prone to develop eating disorders and obesity (1,2), and gender differences in food-preferences and in neuro-humoral regulation of eating behavior have been observed (26). Furthermore, fluctuations in gonadal steroid hormones account for significant

changes in brain activation patterns depending on the menstrual cyclic phase in women (27). As such, women have to be studied on matching days in the late follicular phase. In a study that extends over 4 study visit, this would extend the enrollment period over a minimum of four months, with the associated intra-subject variability and seasonal changes in insulin requirement. We will therefore focus this pilot study on male participants. **Time since diagnosis** is set > 3 years to avoid participants that have persistent endogenous insulin production (honeymoon phase) that would confound the clamp design. The **BMI range** is chosen to exclude participants with underweight or extreme overweight who have alterations brain circuits of intake control (19-24). **Insulin pump use** will allow for tighter metabolic control and provide more detailed data on baseline insulin requirement to inform the insulin clamp design. It will also limit basal insulin on board that may confound plasma insulin levels.

### **Exclusion criteria**

- Insulin resistance (current insulin requirement > 1.5 U/kg/d)
- Insulin requirement < 0.5 unit/kg/day (cut-off for preserved beta-cell function)
- HbA1C  $\geq$  8.0%
- DKA within 2 months
- Frequent hypoglycemia (BG <50 mg/dl), > 3 times per week
- Fluctuations in body weight >10% over preceding year
- Smoking or illicit substance abuse
- High levels of physical activity ( $\geq$ 60 minutes per day,  $\geq$  4 days per week)
- Current weight loss diet
- Medical problems, medications or dietary supplements that may affect metabolism, insulin action, body weight, appetite, energy expenditure, or gastrointestinal absorption (e.g. celiac disease)
- Allergies to compounds or intolerance of the liquid meals
- MRI exclusion criteria
- Other conditions according to self-report that would prohibit participation based and researcher assessment

**Rationale for exclusion criteria.** **Insulin resistance** is not a homogeneous phenomenon and can have different degrees in peripheral tissues and brain. Thus, insulin resistance with the concomitant higher insulin levels would have unforeseen effects on brain activation (e.g. higher insulin exposure, vs. concomitant brain insulin resistance with lower insulin exposure). Participants with overt insulin resistance will therefore be excluded. **Very low insulin requirement and elevated C-peptide** are markers of endogenous insulin production. As endogenous insulin production would confound the clamp design, we will limit the study to participants with minimal to no endogenous insulin production. **Insulin deficiency (high HbA1C, DKA) and hypoglycemia** have known effects on metabolism and intake regulation, and are exclusionary. **Diet and recent weight change, use of medications, or dietary supplements, smoking, physical activity, or adherence to a special diet** may affect metabolism and intake regulation, thereby confounding interpretation of study results.

## **B4. POSSIBLE BENEFITS**

### **Benefits**

Benefits to the participant include medical assessment that might identify a co-existing treatable illness. All clinical, laboratory and MRI studies will be reviewed by a qualified physician or radiologist respectively. We will notify patients and recommend for them to follow up with their physician if significant incidental abnormalities are detected.

The study may provide important information regarding the metabolic and cerebral effects of dietary GI, potentially informing dietary approaches to diabetes care. We believe that the benefits and knowledge to be gained considerably outweigh the minor risks and inconvenience to study participants.

### **Compensation**

Participants will receive \$ 150 upon completion of the pre-test visit, \$ 200 upon completion of test-visit 1, \$ 250 upon completion of test-visit 2, and \$ 300 upon completion of test-visit 3, for a total of \$ 900. Participants in the pilot study will receive \$ 150 upon completion of test-visit 1, \$ 200 upon completion of test-visit 2, and \$ 200 upon completion of test-visit 3, for a total of \$ 600. Compensation will be via check request through the BIDMC Accounts Payable department after each [visit](#). In addition, participants will receive parking vouchers or reimbursement for public transportation.

## **B5. POSSIBLE RISKS AND ANALYSIS OF RISK/BENEFIT RATIO**

The protocol involves only moderate risks and discomforts to the participants. All participants will be screened prior to enrollment to rule-out the presence of any pre-existing or complicating medical condition, as described above. Slight pain and small bruises may be expected from insertion of the iv lines and blood drawing. The participant may feel lightheaded or nauseated during the iv sampling. There is a small chance of allergic reactions after the test meals. Minor discomfort might be caused by resting supine in the MRI scanner. High noise exposure will occur during MRI measurements and will be limited by providing earplugs.

Insulin will be administered iv, posing a potential risk of hypoglycemia. Insulin doses will be similar to participants' typical insulin regimen. We will monitor BG closely, and adjustments to insulin infusion rate will be made promptly. As such, we do not anticipate severe hypoglycemia. However, iv dextrose (D25%) will be available to correct severe hypoglycemia < 50 mg/dl that does not resolve with reduction or discontinuation of insulin infusion. The study physician and a study nurse will be present next to the participant during the entire clamp procedure of the study. During the primed-variable insulin infusion, patients will experience moderate hyperglycemia. Since the standard of care for diabetes treatment does not account for dietary glycemic index, similar hyperglycemia is expected to occur after day to day consumption of processed carbohydrates. However, we will monitor blood glucose and be prepared to intervene if blood glucose exceeds a threshold of 400 mg/dl. This is a safe value as no concurring ketosis or other complications would be expected in this setting.

## **B6. RECRUITMENT AND CONSENT PROCEDURES**

### **Recruitment**

We will recruit participants from the community and diabetes programs at Boston Children's Hospital, and Beth Israel Deaconess Medical Center using a multi-step screening process to assess eligibility prior to enrollment. Advertisements will be posted online and in the community and be distributed to treating physicians.

#### **1. Participant Identification**

##### **1.1. Participating Institutions:**

- Eligible patients will be identified by chart research using data as outlined in 4.1.1.

- Their primary Diabetologist will be informed of study eligibility, and asked to present study information to the patient.
- A letter or email signed by the patient's treating physician will be sent to the patient.
- Interested subjects can contact the study team to arrange for a telephone interview.
- Other patients will be contacted by phone 2-3 weeks after the initial contact to inquire if they would like more information on the study. All calls will take place between 10am-9pm Monday thru Friday, or 10am – 5pm Saturday and Sunday. A telephone script will be used during the conversation or in case a voice message is left (attached).

#### 1.2. Other locations:

- Advertisements will be posted online and in the community and be distributed to physicians.
- Physicians may give study information to potential participants, or
- Physicians may get patients permission to be contacted for the study and will then provide contact information to the study team.
- Participants may contact the study team directly by telephone or email to inquire about the study.

#### 2. Enrollment

- A member of the study team will explain the study and discuss the required time commitment by phone or in person.
- This will be followed by a telephone screening (5 minutes) obtaining data as outlined in 4.1.2.
- At the pre-test visit, participants will lay in the scanner to assess whether they can be positioned correctly. Final eligibility data will be obtained as outlined in 4.1.3.

#### **Consent**

Information about the study design, venous sampling, test meals, MRI technique and scenario, and time commitment will be provided in word and writing to the participant prior to obtaining written consent. Written informed consent will be obtained from all participants by [name] MD PhD, at the screening visit at the BIDMC GCRC.

#### **Subject Protection**

This study has been designed to keep risks to the lowest level possible. A physician will be available on a 24-hr per day basis should any problems arise. The blood sampling and administration of test meals and insulin will be performed under strict supervision of the study physician and iv glucose will be available in the unlikely event of hypoglycemia. All adverse events will be evaluated by the safety officer and the PI within 72 hours (minor or moderate) or 24 hours (serious or fatal).

### **B7. STUDY LOCATION**

#### **Privacy / Physical Setting**

For the preliminary telephone or in-person screening, participants will be asked if they are comfortable answering questions regarding their health and weight or if a callback at a different time is desired. If so, an appointment will be made. Participants will be given general information about the study and asked questions about their age, height, weight, fluctuations in body over preceding year, medical problems, medications, dietary supplements, smoking, illicit substance abuse, level of physical activity, and diet.

The study director will then meet with potential participants at the BIDMC GCRC in a private room to obtain consent. Anthropometric measures, vital signs and iv access will be obtained in a private room in the GCRC. Imaging will take place in the BIDMC imaging facility.

## **B8. DATA SECURITY**

Subject confidentiality will be maintained using unique study identification codes to label blood samples, imaging data and hard copy case report forms. A study identification log will be the only link between a participant's identification codes and identifiable information, such as name and phone number. The log will be kept in a locked file accessible only to study staff for the purposes of enrolling participants. Tracking information will be stored in a separate database that is not linked to results.

Blood samples will be labeled with study identification code, visit number (no date), time point and type of specimen. No identifiable information will be included. Samples will be hand carried and transferred to freezer space at Boston Children's Hospital CRC by study staff.

Imaging data will be labeled with study identification code, visit number and time point. All fMRI reference and difference images will be exported from the DICOM database of the scanner onto a CD or DVD. CDs will be hand carried and transferred to a locked cabinet at [name], Boston Children's Hospital by study staff.

Data collected during the study visit will be recorded on hard copy case report forms to ensure high-quality data and minimize missing information. Case report forms will be hand carried and transferred to a locked cabinet at [name], Boston Children's Hospital by study staff. Data will be entered into an electronic database. A password protected study directory will be established on the server maintained by the Boston Children's Hospital CRP. All database files and SAS analysis files will be stored in this directory. Access to programs and archival datasets will be denied by password to non-staff. All analytic and tracking database files will be backed up daily.

